8.2.5. Clinical Laboratory Safety Analyses

Clinical chemistry, hematology and other laboratory tests are assessed in this study according to the schedule outlined in the Time and Events table (see Section 10.2.1). The following tests will be summarized in clinical laboratory displays:

Clinical Chemistry	Sodium (serum)	Aspartate aminotransferase (AST)	Carbon Dioxide (total)
	Potassium (serum)	Alanine aminotransferase (ALT)	Albumin
	Calcium (albumin corrected)	Phosphate	Blood urea nitrogen (BUN)
		Bilirubin (total and direct/indirect)	Chloride (serum)

Hematology	Platelet count	RBC indices:	Leukocyte (white blood cell) count with Differential
	Erythrocyte (red blood cell) count	Mean corpuscular volume (MCV)	Neutrophils (absolute and segmented)
	Reticulocyte count	Mean corpuscular hemoglobin (MCH)	Lymphocytes
	Hematocrit	Mean corpuscular hemoglobin concentration (MCHC)	Monocytes
		Erythrocytes (red cell) distribution width (RDW)	Eosinophils
			Basophils

Other laboratory tests	Intact parathyroid hormone (iPTH)	Hemoglobin A1c (HbA1c) in diabetic subjects	High-sensitivity C-reactive protein (hs-CRP)
	Urine albumin/creatinine ratio (UACR)		

Summaries of central laboratory Hgb values, HemoCue Hgb values, iron parameter values (serum iron, ferritin, hepcidin, TIBC, TSAT), lipid parameter values (total cholesterol, direct LDL-C, HDL-C), and renal function parameters (eGFR, serum creatinine, UACR) are included in earlier efficacy and safety sections and will not be included with clinical laboratory displays. However, these parameters may be included in PCI summaries.

The clinical chemistry tests performed in this study include ALT, AST and bilirubin. In addition to being summarized with the clinical chemistry values, these laboratory values will be included in some of the Hepatobiliary (liver) displays.

In addition to the visits listed for the laboratory assessments in the Time and Events table (see Section 10.2.1), any of these assessments can be performed at an unscheduled/retest visit or at the follow-up visit at the discretion of the investigator. See Section 10.5.3 for handling of unscheduled values. The laboratory's normal range values will be provided by the central laboratory and potential clinical importance thresholds are defined in Section 10.8.1.

All of the tabular summaries described below will include summaries in SI units; conventional units will also be provided for the following laboratory tests: MCHC, albumin corrected calcium, creatinine, eGFR phosphate, albumin, BUN, total cholesterol, LDL-C, HDL-C, and urine albumin/creatinine ratio. Conversions from SI units to conventional units are included in Section 10.6.4. Hemoglobin summaries will only use conventional mg/dL units. Summaries of reticulocytes will be provided for the total count and percent of total erythrocytes and summaries of neutrophils, lymphocytes, monocytes, eosinophils, and basophils will be provided for total counts and differentials (percent of total leukocytes).

The clinical laboratory safety analyses will be based on the Safety population, unless otherwise specified.

8.2.5.1. Overview of Planned Clinical Laboratory Safety Analyses

Table 11 provides an overview of the planned clinical laboratory safety analyses.

Table 11 Overview of Planned Clinical Laboratory Safety Analyses

Parameter	Absolute				Change from Baseline			
	Summary		Individual		Summary		Individual	
	T	F	F	L	T	F	F	L
Chemistry								
Chemistry Values by Visit	Y				Y			
Worst Case Chemistry Results by PCI Criteria Post-Baseline Relative to Baseline	Y							
Hematology								
Hematology Values by Visit	Y				Y			
Worst Case Hematology Results by PCI Criteria Post-Baseline Relative to Baseline	Y							
Other Laboratory Tests								
Other Laboratory Values by Visit	Y				Y			
Worst Case Other Laboratory Results by PCI Criteria Post-Baseline Relative to Baseline	Y							
Hepatobiliary (Liver)								
Liver Monitoring/Stopping Event Reporting	Y							
Hepatobiliary Laboratory Abnormalities	Y							
Medical Conditions for Subjects with Liver Stopping Events				Y				
Substance Use for Subjects with Liver Stopping Events				Y				
Scatter Plot of Maximum vs. Baseline for ALT		Y						
Scatter Plot of Maximum ALT vs. Maximum Total Bilirubin		Y						

Parameter	Absolute				Change from Baseline			
	Summary		Individual		Summary		Individual	
	T	F	F	L	T	F	F	L
All Laboratory								
All Laboratory Data for Subjects with Any Value of PCI				Y				
All Laboratory Data				Y				
Iron								
Worst Case Iron Results by PCI Criteria Post-Baseline Relative to Baseline				Y				

NOTES:

- T = Table, F = Figure, L = Listing, Y = Yes display generated.
- Summary = Represents TFL related to any summaries (i.e. descriptive statistics) of the observed raw data.
- Individual = Represents FL related to any displays of individual subject observed raw data.

8.2.5.2. Planned Clinical Laboratory Safety Display Details

Clinical Chemistry

Continuous on-treatment values (see Section 10.4.1) will be summarized using mean, standard deviation, minimum, P25, median, P75, and maximum for each scheduled visit and for baseline and end of treatment (see Section 10.6.4) by treatment group..

Continuous on-treatment change from baseline values will be summarized using mean, standard deviation, minimum, P25, median, P75, and maximum for each scheduled visit and for end of treatment (see Section 10.6.4) by treatment group.

The number and percentage of subjects with on-treatment worst case laboratory results relative to PCI criteria (see Section 10.8.1) which are post-baseline relative to baseline will be summarized by laboratory test, category and treatment group. See Section 10.6.4 for additional information on worst case values and PCI categories

Hematology

The displays presented for clinical chemistry laboratory values will also be presented for the hematology laboratory tests listed in Section 8.2.5.

Other Laboratory Tests

The displays presented for clinical chemistry laboratory values will also be presented for the other laboratory tests listed in Section 8.2.5. For reporting purposes, iron parameters will be included in other laboratory tests for PCI displays.

On-treatment hsCRP values will be log-transformed (see Section 10.5.2) and summarized using geometric mean, coefficient of variation, minimum, P25, median, P75, and maximum for each scheduled visit by treatment group.

Percent change from baseline in log-transformed (see Section 10.5.2) on-treatment hsCRP values will be summarized using geometric mean, 95% confidence interval, minimum, P25, median, P75, and maximum for each scheduled visit by treatment group.

Hepatobiliary (Liver)

Please refer to the protocol for details of liver chemistry stopping criteria.

Liver monitoring/stopping events will be summarized by treatment group.

Hepatobiliary laboratory abnormalities will be summarized by treatment group.

Medical conditions for subjects with liver stopping events and substance use for subjects with liver stopping events will be listed.

A scatter plot of maximum on-treatment ALT values versus baseline ALT values will be produced.

A scatter plot of maximum on-treatment total bilirubin (xULN) versus maximum on-treatment ALT (xULN) values will be produced.

All Laboratory

A listing of all laboratory data for subjects with on-treatment laboratory values outside of PCI criteria will be provided.

A listing of all laboratory data will be provided.

Iron parameters

The number and percentage of subjects with on-treatment or post-treatment worst case laboratory results relative to PCI criteria (see Section 10.8.1) which are post-baseline relative to baseline will be summarized by laboratory test, category and treatment group. See Section 10.6.4 for additional information on worst case values and PCI categories.

8.2.6. Vital Signs Analyses

Vital signs are assessed in this study according to the schedule outlined in the Time and Events table (see Section 10.2.1) and include the following assessments:

- Height
- HR
- Weight
- Estimated Dry Weight (only for subjects transitioning to dialysis)

Summaries and analyses of BP values are described in earlier safety sections and will not be included with vital signs summaries. However, BP values will be included in PCI summaries.

The vital signs analyses will be based on the Safety population, unless otherwise specified.

8.2.6.1. Overview of Planned Vital Signs Analyses

Table 12 provides an overview of the planned vital signs analyses.

Table 12 Overview of Planned Vital Signs Analyses

Parameter	Absolute				Change from Baseline			
	Summary		Individual		Summary		Individual	
	T	F	F	L	T	F	F	L
Vital Signs								
Vital Signs by Visit	Y				Y			
Summary of Worst Case Vital Signs Results by PCI Criteria	Y							
All Vital Signs for Subjects with Any Value of Potential Clinical Importance				Y				

NOTES:

- T = Table, F = Figure, L = Listing, Y = Yes display generated.
- Summary = Represents TFL related to any summaries (i.e. descriptive statistics) of the observed raw data.
- Individual = Represents FL related to any displays of individual subject observed raw data.

8.2.6.2. Planned Vital Signs Display Details

Vital sign values will be summarized using mean, standard deviation, minimum, P25, median, P75, and maximum for each scheduled visit and for baseline and end of treatment by treatment group.

Vital sign change from baseline values will be summarized using mean, standard deviation, minimum, P25, median, P75, and maximum for each scheduled visit and for end of treatment by treatment group.

The number and percentage of subjects with on-treatment or post-treatment worst case vital sign results relative to PCI criteria (see Section 10.8.1) which are post-baseline relative to baseline will be summarized by test, category and treatment group. See Section 10.6.4 for additional information on worst case values and PCI categories.

A listing of all vital signs data for subjects with on-treatment vital signs values outside of PCI criteria will be provided.

8.2.7. Electrocardiograms

Electrocardiograms (ECGs) will be read locally and ECG data will not be included in summary tables or individual subject listings.

8.2.8. Pregnancies

A listing of all subjects who became pregnant during the study will be included.

8.2.9. Other Safety Analysis

Clopidogrel Analysis

The following analyses will be conducted to confirm the effect of clopidogrel co-administration.

The treatment emergent AEs and SAEs will be summarized with the number, percentage and rate per 100 person-years, by clopidogrel co-administration, treatment group, and system organ class and preferred term. Clopidogrel co-administration is defined as subjects who use clopidogrel once or more during the on-treatment state for concomitant medications (see Section 10.4.1).

The number and percentage of subjects with a >1 g/dL increase in Hgb over 2 weeks (assessed at Week 2 and Week 4), or a >2 g/dL increase in Hgb within any 4-week period from Week 4 to Week 52, will be summarized by visit by clopidogrel co-administration, and by treatment group using HemoCue Hgb values. This summary will be presented using evaluable Hgb values only (see Section 10.6.3).

The number and percentage of subjects with a >2 g/dL increase in Hgb within any 4-week period from Week 4 to Week 52, will be summarized by visit by clopidogrel co-administration, and by treatment group using central laboratory Hgb values. This summary will be presented using evaluable Hgb values only (see Section 10.6.3).

For the above two tables, the Clopidogrel co-administration groups are baseline clopidogrel users, new clopidogrel users, and clopidogrel non-users during the first year of the study. Baseline clopidogrel users, defined as subjects who use clopidogrel at randomization, will be summarized only at Week 2 and Week 4 for the HemoCue Hgb table, and only at week 4 in the central laboratory Hgb table. New clopidogrel users are defined as subjects who started clopidogrel after randomization during the on-treatment state for concomitant medications (see Section 10.4.1) in the first year of the study. If they started clopidogrel within two weeks of a scheduled visit (i.e. visit date - 2w < clopidogrel start date \leq visit date + 2w), they will only be summarized in the following scheduled visit. Clopidogrel non-users are subjects who do not use clopidogrel neither at randomization nor anytime during the on-treatment state for concomitant medications (see Section 10.4.1) in the first year of the study.

The number and percentage of subjects with a Hgb value ≥ 12 g/dL during the study will be summarized by clopidogrel co-administration, and by treatment group using evaluable Hgb values (see Section 10.6.3). Clopidogrel co-administration is defined as subjects who

use clopidogrel once or more either at randomization or during the on-treatment state for concomitant medications (see Section 10.4.1).

The number and percentage of subjects who had dose adjustments (decreases, increases, no change) will be summarized at Week 2 and Week 4 by baseline clopidogrel co-administration, and by treatment group. The number of dose decreases per subject will be summarized for baseline clopidogrel users, using mean, standard deviation, minimum, P25, median, P75, and maximum by baseline clopidogrel use, and by treatment group, for Day 1 to Week 12. Baseline clopidogrel co-administration is defined as subjects who use clopidogrel at randomization.

The number and percentage of subjects had dose adjustments (decreases, increases, no change) will be summarized for new clopidogrel users, who started clopidogrel after randomization, during the on-treatment state for concomitant medications (see Section 10.4.1), by treatment group. If they started clopidogrel within two weeks of a scheduled visit (i.e. visit date - 2w < clopidogrel start date \leq visit date + 2w), they will be summarized in the following scheduled visit. The number of dose decreases per subject will also be summarized for these new clopidogrel users using mean, standard deviation, minimum, P25, median, P75, and maximum by clopidogrel use, and by treatment group, for clopidogrel use start date to clopidogrel use + Week 12.

The median assigned dose by treatment, by clopidogrel co-administration, and visit will be displayed graphically for each scheduled study visit from day 1 to week 52 using a line plot. The line plot of median assigned dose along with the first and the third quartiles by time will include vertical reference lines to identify the EP as well as the number of subjects by treatment group contributing to each median value. This plot will be overlaid on a graph of corresponding mean Hgb values by visit. Clopidogrel co-administration here is defined as subjects who use clopidogrel once or more, at randomization, or during the on-treatment state for concomitant medications (see Section 10.4.1) in the first year of the study.

A box plot of evaluable Hgb change at Week 2 from baseline, by baseline clopidogrel co-administration and treatment group will be produced. Baseline clopidogrel co-administration is defined as subjects who use clopidogrel at randomization. Hemocue Hgb will be used in this figure, since only Hemocue Hgb is available at Week 2. This box plot will be repeated at Week 4 using evaluable Hgb, by baseline clopidogrel co-administration and treatment group.

A box plot of 4-week changes in evaluable Hgb after starting clopidogrel will also be produced by treatment for new clopidogrel users, who started clopidogrel after randomization, during the on-treatment state for concomitant medications (see Section 10.4.1). The 4-week change in evaluable Hgb will be estimated by calculating the change at the first visit after starting clopidogrel, from the previous visit at least 4 weeks before. The first visit after starting clopidogrel is defined as the first visit (scheduled or unscheduled) after clopidogrel start that was at least two weeks after the start date of clopidogrel.

COVID-19 Analyses

The following COVID-19 related displays will be provided.

A summary of the number and percentage of subjects for the following assessments will be produced: Case Diagnosis, COVID-19 Test performed, and Results of the COVID-19 test.

Summaries of characteristics of COVID-19 AEs will include the number, percentage of subjects having at least one occurrence, the outcome, maximum intensity, and the duration of the AE summarized by treatment group. For each count, a subject will be summarized as follows:

- Outcome: The subject will be counted within a category if there is at least one specific AE in that category.
- Maximum intensity: The specific AE with the maximum intensity will be counted for this purpose. For example, a subject will be counted in the ‘severe’ category if there is at least one specific AE with severe intensity. A subject will be counted in the ‘moderate’ category if there is at least one specific AE with moderate intensity and there is no specific AE with severe intensity.
- Duration of the occurrence (days): AE resolution date – AE onset date/AE worsening date + 1 for the occurrence

A summary of the number and percentage of subjects with COVID-19 symptoms will be produced.

A summary of exposure adjusted incidence rates over time (see Section 10.6.4) will be produced by treatment group for any treatment emergent AE, any treatment emergent SAE, and any treatment emergent Severe AE, for two periods – pre COVID-19 pandemic and during COVID-19 pandemic. The summary will be produced overall, by Country, Region, Sex, and by Age at randomization (Grouping 2) (see Section 10.10.1). A summary of exposure adjusted incidence rates by treatment group will also be produced for Common (>5%) AEs for two periods – pre COVID-19 pandemic and during COVID-19 pandemic.

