Treatment emergent	
If AE onset date or AE worsening date is on or after treatment start date & on or before the last non-zero dose date plus 1 day. Treatment Start Date \leq AE Start Date \leq Last Non-Zero Dose Date + 1 day Treatment Start Date \leq AE Worsening Date \leq Last Non-Zero Dose Date + 1 day AE worsening during treatment emergent will be defined relative to the maximum intensity of AE prior to randomized treatment start date. AE worsening date is the first date in the treatment emergent period, when AE intensity increased relative to the maximum intensity of the AE prior to randomized treatment start date.

Follow-up	
If AE onset date or AE worsening date is after the last non-zero dose date plus 1 day. AE Start Date $>$ Last Non-Zero Dose Date + 1 day AE Worsening Date $>$ Last Non-Zero Dose Date + 1 day AE worsening during follow-up will be defined relative to the maximum intensity of AE prior to randomized treatment start date. AE worsening date is the first date in the follow-up period, when AE intensity increased

	relative to the maximum intensity of the AE prior to randomized treatment start date.
Onset /Worsening Time Since 1 st Dose (Days)	If Treatment Start Date > AE Onset Date = AE Onset Date - Treatment Start Date If Treatment Start Date ≤ AE Onset Date = AE Onset Date - Treatment Start Date + 1 If Treatment Start Date > AE Worsening Date = AE Worsening Date - Treatment Start Date If Treatment Start Date ≤ AE Worsening Date = AE Worsening Date - Treatment Start Date + 1 Missing otherwise.
Onset/Worsening Time Since Last Dose (Days)	If Last Non-Zero Dose Date ≤ AE onset date: AE onset date – last non-zero dose date +1 If Last Non-Zero Dose Date > AE onset date: AE onset date – last non-zero dose date If Last Non-Zero Dose Date ≤ AE worsening date: AE worsening date – last non-zero dose date +1 If Last Non-Zero Dose Date > AE worsening date: AE worsening date – last non-zero dose date Missing otherwise.
Duration (Days)	AE Resolution Date – AE Onset Date/AE Worsening Date + 1
Drug-related	If relationship is marked 'YES' on eCRF or if the value is missing.

NOTES:

- AEs that occur or worsen during interruptions of randomized study treatment will be classified as treatment emergent and post-randomization.

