10.4.1.5. Treatment States for Concomitant Medications (Other Than Iron Use Summaries)

Pre-treatment medications are those taken (i.e., started) before the start date of randomized treatment. On-treatment medications are those taken (i.e., started or continued) at any time between the randomized treatment start date and the last non-zero dose date + 1 day, inclusive. Pre-treatment medications that were continued during this on-treatment period are also considered to be on-treatment medications. Post-treatment medications are those taken (i.e., started or continued) at any time after the last non-zero dose date + 1 day. On-treatment medications that were continued during this post-treatment period are also considered to be post-treatment medications. Post-randomization medications are those taken (i.e., started or continued) at any time on or after the randomization date.

It will be assumed that the medication has been taken on the date in which it is reported as started or stopped. Also, for any medication starting on the same date as randomized treatment, it will be assumed that the medication was taken after the subject started taking randomized treatment.

Illustrations of the pre-treatment, on-treatment, and post-treatment treatment states are included below:

	Pre-treatment	On-treatment			Post-treatment	Pre-treatment medication	On-treatment medication	Post-treatment medication
		Randomized Treatment Start Date		Last Non-zero Dose Date + 1 Day	Last Non-zero Dose Date + 2 Days			
(a)	x——x					Y	N	N
(b)	x——		——x			Y	Y	N
(c)	x——		——		——x	Y	Y	Y
(d)			x——x			N	Y	N
(e)			x——		——x	N	Y	Y
(f)					x——x	N	N	Y
(g)	?——x					Y	N	N
(h)	?——		——x			Y*	Y	N
(i)	?——		——		——x	Y*	Y*	Y
(j)	x——		——		——?	Y	Y**	Y**
(k)			x——		——?	N	Y	Y**
(l)					x——?	N	N	Y
(m)	?——		——		——?	Y***	Y***	Y***
(n)	x——	x				Y	Y	N
(o)	?——	x				Y*	Y	N
(p)		x	——x			N	Y	N
(q)		x	——	x		N	Y	N
(r)				x	——x	N	Y	Y
(s)				x	——?	N	Y	Y**
(t)					x——x	N	N	Y
(u)					x——?	N	N	Y
(v)			x——	——	x	N	Y	Y

x = start/stop date of medication

? = missing start/stop date of medication

* If a medication is stopped On-treatment or Post-treatment and no start date is recorded it will be assumed that the medication was ongoing from the Pre-treatment phase

** If a medication is started Pre-treatment or On-treatment and no stop date is recorded then usage will be assumed to be ongoing for the remainder of the study

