10.6.2.4. Prior and Concomitant Medications

Prior and Concomitant Medications
Non-randomized ESA use during treatment period

 • Subjects will be considered to have non-randomized ESA use during the treatment period if they have any ESA concomitant medication records with one of the following two reasons for medication: 
 ○ Non-randomized ESA treatment in addition to randomized treatment ○ Non-randomized ESA treatment instead of randomized treatment
Duration of non-randomized ESA use during treatment period

 • If there is only one concomitant medication record of non-randomized ESA use during the treatment period, then: 
 ○ Duration (days) = earliest of (concomitant medication record end date, last non-zero dose date + 1 day) – latest of (concomitant medication start date, treatment start date) + 1 day • If there are multiple concomitant medication records of non-randomized ESA use during the treatment period, then the duration of non-randomized ESA use will add the durations for all records, subtracting any overlapping days that may exist between the multiple records.
Clopidogrel start date for new clopidogrel users

 • New clopidogrel users are subjects who did not use clopidogrel on randomization day, but started their clopidogrel use after randomization during the on-treatment state for concomitant medications. To determine the start date of clopidogrel for the new users, only the first clopidogrel record during the on-treatment state for concomitant medications will be considered. The start date will be the first day subjects on both clopidogrel and randomized treatment.

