
 2. Order SOCs (small to large) according to the minimum FDR adjusted p-value observed for treatment differences across PTs within SOC. 3. Perform the FDR method on the minimum adjusted p-values from Step 2. 4. Select SOCs with FDR adjusted p-value from Step 3 <0.10. 5. Apply a single FDR adjustment to all unadjusted p-values belonging to all PTs from SOCs identified in Step 4. A threshold of FDR adjusted p-values <0.10 will be used to flag PTs that warrant further investigation. 
Note that 0.10 is recommended as a reasonable multiplicity adjustment for 0.05.

General Definitions

 • Post-Randomization last contact date for censoring (subjects not having AE) will be defined as the study completion date.

 • Treatment emergent last contact date for censoring (subjects not having AE) will be defined as follows: 
 ○ 1 day after the last non-zero dose date (last non-zero dose date + 1) for subjects not having treatment emergent AE and continuing on study past (last non-zero dose date + 1) ○ Last non-zero dose date for all other subjects

 • AE Patient Years: (Cumulative total of time to AE for subjects who have the AE + Cumulative total of censoring time for subjects without the AE) / 365.25 
 ○ For treatment emergent AEs, the start date of the patient years value for each subject should be the treatment start date. ○ For post-randomization AEs, the start date of the patient years value for each subject should be the randomization date. ○ For follow-up AEs, the start date of the patient years value for each subject should be 2 days after the last non-zero dose date (last non-zero dose date + 2).

 • Incidence Rate (per 100 patient years): $(100 * \text{Number of subjects with at least 1 AE}) / \text{AE person years}$

 • For the analysis of the time to AE onset/worsening, if the AE onset/worsening date is missing then the time to AE onset/worsening will be counted as 1 day.

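### The clopidogrel AE/SAE tables class subjects by any on-treatment use, so events and person-time before the first clopidogrel dose are counted as co-administered

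*SAP*

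**What the plan says.** Section 8.2.9 opens the clopidogrel displays with their aim: "The following analyses will be conducted to confirm the effect of clopidogrel co-administration". The first display is the safety table: "The treatment emergent AEs and SAEs will be summarized with the number, percentage and rate per 100 person-years, by clopidogrel co-administration", then by treatment group, system organ class and preferred term. Its exposure rule is "Clopidogrel co-administration is defined as subjects who use clopidogrel once or more during the on-treatment state for concomitant medications".

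Three definitions elsewhere in the SAP determine what that rule does:

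- Section 10.4.1.5, on the medication state: "On-treatment medications are those taken (i.e., started or continued) at any time between the randomized treatment start date and the last non-zero dose date", extended by one day. Clopidogrel started at any point in that span qualifies, and so does clopidogrel continued from before randomization.
- Section 10.4.1.4, on when an AE is treatment emergent: "If AE onset date or AE worsening date is on or after treatment start date", up to the last non-zero dose plus one day. Clopidogrel dates play no part.
- Section 10.6.4.4, on the denominator: "For treatment emergent AEs, the start date of the patient years value for each subject should be the treatment start date".

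Section 8.2.4 keeps the AEs and SAEs associated with non-fatal MI and non-fatal stroke in the AE summaries.

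A later display in Section 8.2.9, of subjects with Hgb at or above 12 g/dL, also uses ever-use. Its users are those who "use clopidogrel once or more either at randomization or during the on-treatment state for concomitant medications".

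**The concern.** The section asks what happens when clopidogrel is taken together with randomized treatment. A table can answer that only if the events in the co-administered column happened during joint use. Here a subject who has an MI, starts clopidogrel a few days later and stays on randomized treatment is a user for the whole treatment period, and the MI is counted in the user column.

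Clopidogrel is commonly started because of an ischaemic event. That is ordinary clinical reasoning and not SAP text, but it means the misplaced events would not be a random sample: they would be concentrated in the cardiovascular terms of most interest. The misplacement itself needs no such premise, because it affects any AE that comes before first use.

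At stake is the reading of the only AE displays in the clopidogrel analysis. A reader could take a reversed sequence of events as a cardiovascular signal, or dismiss a real signal as explained by the reason for prescribing.

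**Working it through.** **The plan's own figure.** The SAP states none for this analysis, so there is nothing to reproduce.

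**Step 1: follow one subject through the definitions.** Randomized treatment starts on day 1, a first MI occurs on day 300, clopidogrel starts on day 302, and randomized treatment continues.

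- Medication state: started before the last non-zero dose plus one day, so the subject is a user.
- AE: onset after treatment start, so the MI is treatment emergent and enters the user column.
- Person-years: for a subject with the AE, Section 10.6.4.4 counts time from treatment start to the AE, here 300 days, all before clopidogrel.

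This subject adds one MI and 300 days to the co-administered MI rate, with no day of joint exposure in either.

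**Step 2: compare with the neighbouring displays.** The Hgb-increase tables in Section 8.2.9 separate baseline users, new users and non-users and apply a start-date rule. The dose-adjustment summaries use clopidogrel use at randomization, or follow new users from clopidogrel start. The box plots use baseline use, or change after clopidogrel start. Section 10.6.2.4 derives a date for new users: "The start date will be the first day subjects on both clopidogrel and randomized treatment". None of this is applied to the AE/SAE tables.

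**Step 3: illustrate the size with no true clopidogrel effect.** All inputs are assumed, none from the SAP: MI rate 3 per 100 person-years, 2 years on treatment, new clopidogrel for other reasons 1 per 100 person-years, baseline use b = 5 to 15%, and a share q = 25 to 75% of subjects with an MI starting clopidogrel straight after it while on randomized treatment.

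Middle case by hand (b = 10%, q = 50%):

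- P(MI) = 1 − exp(−0.06) = 0.0582. P(start for another reason) = 1 − exp(−0.02) = 0.0198.
- Users: 0.10 + 0.90 × [1 − 0.9802 × (1 − 0.5 × 0.0582)] = 0.1435.
- MIs among users: baseline users 0.10 × 0.0582 = 0.0058; started after the MI 0.90 × 0.5 × 0.0582 = 0.0262; other new users 0.90 × 0.0198 × 0.0582 × 0.5 = 0.0005. Total 0.0325.
- Users with an MI: 0.0325 / 0.1435 = 22.7%.
- Non-users with an MI: 0.90 × 0.9802 × 0.0582 × 0.5 / (1 − 0.1435) = 3.0%.
- Share of the users' MIs that came before clopidogrel: about 0.0262 / 0.0325 = 81%.

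Simulation of 2,000,000 subjects per scenario, extremes and middle:

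| Baseline use, share starting after MI | Users, MI per 100 PY | Non-users, MI per 100 PY | Rate ratio | Users' MIs before clopidogrel |
|---|---|---|---|---|
| 15%, 25% | 6.47 | 2.26 | 2.9 | 58% |
| 10%, 50% | 12.80 | 1.53 | 8.4 | 81% |
| 5%, 75% | 25.78 | 0.77 | 33 | 92% |

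The true ratio is 1 in every row.

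**Step 4: the same data, classified differently.** By clopidogrel use at onset, the ratio over all nine scenarios is 0.99 to 1.01. By use at randomization it is 0.98 to 1.01. The simulation started clopidogrel strictly after the MI, so it does not test same-day starts or imputed dates.

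**The case against.** Several counter-arguments have force.

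- **The tables are descriptive.** They carry no test and no decision rule. This stands and limits the weight of the point.
- **Baseline users are correctly placed.** Under the assumptions above, baseline users are 84%, 70% and 46% of the user group in the three tabulated scenarios, and those who started because of an MI are about 7%, 18% and 38%. A reader might infer that most users are there because of an on-study event. The SAP gives nothing to support that, and the size must be left open. Adding stroke would raise these shares.
- **The rule is the same in both arms.** A reader might infer that a true interaction with daprodustat would be hidden. That is not shown: the simulation covers users against non-users, not the difference between arms across those groups. What can be said is that comparing arms among users conditions on something that happened after randomization and mixes in unexposed events and time.
- **Not every such event is affected.** If clopidogrel starts more than one day after the last non-zero dose, the subject is not a user. Events that are fatal before clopidogrel could be started fall to non-users, which pulls the other way.
- **Hgb at or above 12 g/dL is different.** A reader might extend the reversed-sequence argument to that display. Nothing suggests that a high Hgb prompts clopidogrel, and the display has no person-years. Only dilution remains.

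That timing is handled well in most of Section 8.2.9 is also true. It shows that the remedy is at hand, but it does not correct the AE/SAE tables.

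**Conclusion.** The point holds for the AE/SAE tables. As defined, they credit to co-administration all of a user's treatment-emergent events and person-time, including what came before clopidogrel. The user versus non-user contrast is biased towards a cardiovascular excess in users, and the between-arm comparison among users is contaminated with unexposed events and time.

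The misplacement follows from the SAP's definitions alone. The cardiovascular direction rests on the clinical assumption that ischaemic events lead to clopidogrel. The illustrative ratios of 2.9 to 33 rest entirely on assumed inputs and should not be read as a forecast: the real size depends on how many users are baseline users and how many are new. For Hgb at or above 12 g/dL the fault is limited to diluted exposure. The co-primary and principal secondary analyses are not touched. The change is worth making before the tables are produced, but no main conclusion of the trial depends on it.

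**What to change.** Choose one rule for the AE/SAE tables in Section 8.2.9.

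1. **Use at randomization.** Tabulate by the baseline definition already used in the same section. Subjects who start clopidogrel later stay in the column for non-use at randomization; removing them would again select on a later event. This needs only a wording change. The price is less exposed person-time and some exposed time in the comparison column.
2. **Exposure at onset.** For new users, count an AE as co-administered only if onset is after, not on, the start date in Section 10.6.2.4 and during joint use. An event on the start date may be the one that prompted clopidogrel. Put earlier events and person-years in the non-exposed column, and state where time after clopidogrel stops belongs. Flag subjects whose clopidogrel start date was imputed: Section 10.7.2.1 sets a missing day to the first and a missing month to January, which can place the start before the triggering event. The price is less exposed person-time and a new derivation of joint-use end dates and gaps.

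For Hgb at or above 12 g/dL, show baseline and new users separately, and for new users count only values after clopidogrel start.

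No new data collection is needed for any of this.
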